Effectiveness analyses will use intention to treat methods. To compare overall effectiveness, generalized linear mixed models (GLMM) will be used to determine if there are differences in effectiveness between individuals receiving TES and eTAU over time. Missing data will be examined for potential non-ignorable mechanisms, and will be managed through multiple imputation. Additional covariates will also be included to identify any substantive changes in the service, technologies, and/or implementation plan as a result of optimization. We will examine moderation of treatment arm by strata (postpartum or antenatal), and present results within each strata.

Moderation of TES on effectiveness. We will examine any moderation of the effect of treatment arm on depressive symptoms by race, ethnicity, age, health status, substance/alcohol use, mobile phone competence, or other mental health treatments, in individual GLM models, by estimating a treatment by moderator interaction in predicting end of treatment depression scores adjusting for baseline levels of depression.

Power. Although a pilot study, we provide an estimate of effect that we can detect with 100 randomized participants, as well as within strata of 80 and 20. As power calculations for repeated measures involve correlations over time which are speculative at this point, we provide effect size estimates for 12 month PHQ-9 scores based on an independent t-test. We have 80% power to detect an effect size of 0.58 for the entire cohort – a difference in PHQ-9 scores between eTAU and TES of 2.9 assuming a SD of 5; and effect sizes of 1.41 and 0.65 in antenatal and postpartum populations, which correspond to differences of 7.03 and 3.26 on the PHQ-9).

PROVISIONS TO MONITOR THE DATA TO ENSURE THE SAFETY OF PARTICIPANTS

Data and safety monitoring of participants will be monitored by the Principal Investigator, [name], who have primary responsibility for monitoring and will do so on a weekly basis during their planned meetings. [name] will regularly review all data and adverse events and will report all serious adverse events to the Northwestern University Institutional Review Board Requirements. Second, any reporting of significant mental or physical health-related symptoms by the participant to the study team will result in appropriate referrals to the participant's clinician or other appropriate facilities.

The PIs, with the support of the entire research team, will follow procedures outlined under the "Protection of Human Subjects" document that will serve as part of the quality control process for data confidentiality. The PIs will engage with the study team and case managers on a regular basis to ensure data accuracy and protocol adherence.

To ensure the validity and integrity of study data, the PIs, assisted by the Center statistical team, will oversee data management and data checking. Study data are accessible at all times for the PIs, the biostatistician, and all relevant Co-Is to review. The biostatistical team and study manager will conduct

STU#:00211815

analyses of accrual, drop-outs, protocol deviations on a monthly basis initially, which may drop to quarterly once we are confident that procedures are functioning adequately.

[name] will review adverse events (AEs) and serious adverse events (SAEs) individually in real-time and in aggregate at each DSMB meeting (not less than annually). They will review the information and make judgments on whether the events were study-related and the severity of the adverse event. These events will be recorded on an Adverse Event Form. Depending on the consensus of the review, further action will be taken to revise the intervention to avoid future events or the study will be stopped if significant harm is anticipated. The PIs ensure all protocol deviations, AEs, and SAEs are reported to the IRB and the NIMH program officer according to the applicable regulatory requirements.

For this study, the following standard AE definitions are used:

Adverse event: Any unfavorable and unintended sign or symptom temporally associated with the use of digital mental health interventions, regardless of whether it is considered related to intervention.

Serious Adverse Event: Any AE that results in any of the following outcomes:

- Death
- Life-threatening situation
- Event requiring inpatient hospitalization or prolongation of existing hospitalization
- Persistent or significant disability/incapacity

AEs are graded according to the following scale:

- Mild: An experience that is transient, and requires no special treatment or intervention. The experience does not generally interfere with usual daily activities.
- Moderate: An experience that is alleviated with simple therapeutic treatments. The experience impacts usual daily activities.
- Severe: An experience that requires therapeutic intervention. The experience interrupts usual daily activities. If hospitalization (or prolongation of hospitalization) is required for treatment it becomes an SAE.

The study uses the following AE attribution scale:

- Not related: The AE is clearly not related to the study procedures (i.e., another cause of the event is most plausible and/or a clinically plausible temporal sequence is inconsistent with the onset of the event).
- Possibly related: An event that follows a reasonable temporal sequence from the initiation of study procedures, but that could readily have been produced by a number of other factors.
- Related: The AE is clearly related to the study procedures.

SAEs and specific treatment-associated AEs are reported to the IRB and NIMH program officer within 24 hours.

Data Safety Monitoring Board (DSMB)

The DSMB will be chaired by [name], from Kaiser Permanente, Seattle. [name] is a well-respected mental health researcher. As chair of the DSMB, [name] will appoint additional board members as needed and will determine the meeting schedule. That said, we expect that the DSMB will meet twice in the first year of the trial and once in the final year. The PIs, [name], and [name] (biostatistician) will be present to facilitate the flow of information, however they will not be voting members.

PROVISIONS TO PROTECT THE PRIVACY INTERESTS OF PARTICIPANTS

Potential participants will be identified by the CM. Prior to being consented, candidates will receive information about the study. Candidates who decline the consent procedure or who are screened out will have any identifying information removed from study records. Consent for the study will then be managed by research study personnel, rather than the CM. The study team will not release the identity of any participant to any non-authorized individual, except as is necessary for participant safety or regulatory review.

STU#:00211815

ECONOMIC BURDEN TO PARTICIPANTS

There will be no cost to participants to receive the TES. It is possible that some participants might have very limited data plans, and the use of IntelliCare apps will cause them to exceed their data limit resulting in fees. IntelliCare apps do not use unusually large amounts of data, so this is an unlikely occurrence, and the study team asks about participant data plans and will inform participants of the expected data usage prior to downloading the apps. There are no procedures that will be billed to insurance.

CONSENT PROCESS

Participants who are referred to the trial by their Care Manager will be verbally screened for eligibility. If participants screen eligible, they will be directed to a digital version of the consent form. The consent form will be administered via Northwestern University's instance of REDCap. Subjects will read through the consent form, answer a series of questions to assess comprehension, and agree to participate by checking a box, typing in their name, and signing electronically. Once the consent is submitted, study staff will review the participant's digital file to ensure that the consent form was signed and the comprehension questions were answered correctly. If a participant answers any of the consent comprehension questions incorrectly, a research assistant will follow up to review that section of the consent form and explain the correct answer. After the consent process is finalized, the participant will be able to access a link to complete the baseline self-report measures along with Instructions for downloading the IntelliCare applications.

NON-ENGLISH SPEAKING PARTICIPANTS

Non-English speaking participants will not be enrolled.

PROTECTED HEALTH INFORMATION (PHI AND HIPAA)

HIPAA authorization language has been included in the study consent form.

The following PHI may be gathered from the patient's medical record:

- Medical history
- Problem list (which may include things like HIV testing results, substance abuse information, and mental health information).
- Records about medication or drugs
- Mental Health information: mental health diagnoses and assessment information, and information about encounters with mental health providers.
- Obstetrics info

Any data that is gathered through the patient's electronic medical records (EMR) will be deidentified. We will store the EMR data separate from the self-report data with identifiers.

QUALIFICATIONS TO CONDUCT RESEARCH AND RESOURCES AVAILABLE

The research staff at CBITs have extensive experience conducting remote-delivered mental health interventions. [name] has experience with successful recruiting and retaining perinatal individuals in longitudinal research studies. With 90 perinatal individuals with PPD currently engaged in COMPASS care along with 30-50 patients referred to COMPASS monthly (conservatively 30% of whom have a primary diagnosis of PPD), successful recruitment into the pilot randomized trial is highly feasible. The COMPASS and CBITs staff have been working closely on the development of this project for several months, and are working to put the resources in place to conduct this study. The services being provided in this study are a supplement to standard care, and the CM will continue to provide all standard care services to patients who enroll in this study.

MULTI-SITE RESEARCH

Table 6. Research Sites and Vendors

Site	Role	Approvals
------	------	-----------

STU#:00211815

Northwestern University (NU)	
NU will serve as the lead site for this study. Study team members will be responsible for maintaining current versions of the protocol, consent documents, and other IRB materials. NU study team members will be responsible for screening and consenting study participants, collecting outcome data, delivering and supervising the TES, disbursing subject payments, managing suicidality assessments, and analyzing study data. NU staff will facilitate regular project meetings with participating sites and will be responsible for communicating procedural changes, emergent issues, interim results, and study status updates. NU will be responsible for ensuring that all sites involved in data handling have executed the appropriate agreements.
	IRB protocol number STU00211815
Adaptive Health	
Software Development/Maintenance: Adaptive Health established a Master Service Agreement with Northwestern University to make their IntelliCare platform available for use in delivery of the TES.
 
Data Storage/Retention: Adaptive will store data on their secure servers during the trial and transfer it to NU at the end of the trial. Upon termination of the study, Adaptive Health will erase participant identifiers and retain only de-identified data which will be used to improve the IntelliCare product (per section 19 of the Master Service Agreement).
	
The following executed agreement between NU and Adaptive Health has been uploaded to the eirb+ portal:
 
Northwestern University and Adaptive Health Master Services Agreement_Fully_Executed.pdf

Women and Infants Hospital (WIH)	
[name] is moving from Northwestern University to Women and Infants Hospital (WIH) on 6/8/22. [name] will retain her role as primary investigator at Women and Infants Hospital.
 
[name] has a faculty appointment at Brown University. However, her research is happening at WIH, thus this protocol reflects work that is being done at WIH.
 
One institution will act as external collaborating site: Women and Infants Hospital. Northwestern University will serve as the IRB of Record for each relying site.
 
Site: Women and Infants Hospital Site PI: [name], MPH Address: Women and Infants Hospital -- Care New England [name]
 
Activities to be performing: full research protocol as listed in this protocol.
 
Of note: No activities will occur at an external site until they obtain approval from their local IRB, or the NU IRB and external sites fully execute (complete and sign) a reliance agreement. External study
	12/19/2022: The study team received consultation from the IRB. The single IRB letter of support states Brown University, but it was clarified during the consultation that all research activities would take place at Women and Infants Hospital. The IRB has noted this in their files.

STU#:00211815

	
teams will obtain sign-offs or permissions per their local policies. We will provide IRB approval letters from external sites, documentation that IRB review at external sites is unnecessary, or fully executed reliance agreements when available with accompanying protocol updates via modification requests in eIRB+. We will report non-compliance with the study protocol or applicable requirements per local policy.
 
 • Is reliance mandated per federal guidelines or sponsor requirements? 
 ◦ Federal guidelines. • If this research is federally funded, who is the prime awardee? 
 ◦ Women's and Infant Health is the prime awardee. • Who is the proposed IRB of Record for all participating sites? 
 ◦ Northwestern University. • What type of reliance agreement will be used? 
 ◦ IRB Authorization Agreement (IAA) • When will institutions or individuals be onboarded? When NU is the proposed IRB of Record, we prefer to review the NU site and overall study scope first, and onboard institutions or individuals in subsequent modifications via fully executed reliance agreements. Onboarding during the initial review process may delay initial approval. 
 ◦ Institutions will be onboarded after this modification is approved. This IRB was initially an approved single-site trial; then, a PI left to another institution (WH) which is why this is now a multisite study. • How will you communicate IRB approval of modifications to study procedures to relying institutions or individuals, and ensure approval before implementation? 
 ◦ [name], Project Manager, will be updating relying sites directly. He has direct access to each relying site IRB system. • How will you keep participating institutions or individuals abreast of any problems, interim results, or the eventual closure of the study? 
 ◦ [name], Project Manager, will be the project manager for the relying site and will oversee all research activities; thus, he will be the one providing updates as needed. • How will you manage information to protect 	
--	---	--

STU#:00211815

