We will compare the TES to an eTreatment As Usual (eTAU) consisting of current care plus access to a website [<http://compass-care.northwestern.edu/>] that will provide content specific to perinatal depression.

We will utilize a randomized clinical trial (RCT) to compare a technology enabled service (TES) intervention to enhanced treatment as usual (eTAU) within antenatal and postpartum women. Randomization will occur at the patient level. It is not feasible to mask participants or providers.

The primary effectiveness outcome is depression severity. Secondary outcomes are anxiety, and satisfaction with care.

Aims

Aim 1: Conduct a pilot Optimization-Effectiveness-Implementation (OEI) hybrid trial of a Technology Enabled Service (TES) for the treatment of depression compared to enhanced treatment as usual (eTAU).

Aim 2: Experimental therapeutics aims. Analyses will explore the mediating effects of the CM dashboard features that support the CM's treatment activities and workflow, including tracking symptom response, managing the stepped care processes, and communicating care plans. We will also explore the moderating effects of race, ethnicity, income, age, anxiety symptom severity, and mobile phone competence on the depression outcome.

BACKGROUND

Note: The "Background" section has been significantly reduced to create a more succinct protocol document. The original grant submission with the full background information is available upon request.

1. Perinatal depression is common and associated with adverse maternal and child outcomes.¹⁻⁵

Glossary of Terms:

- a. **Perinatal:** relating to the time, usually a number of weeks, immediately before and after birth.
 - a. **Antenatal:** before birth; prenatal.
 - b. **Postpartum:** The period just after delivery, as with postpartum depression. Postpartum refers to the mother, and postnatal to the baby.

2. Myriad barriers to effective treatment exist.⁶⁻¹¹

3. Collaborative Care (CC) represents an innovative health systems approach to depression treatment.¹²⁻²⁰

4. Perinatal Depression poses unique care challenges.²¹⁻²²

5. Significant gaps exist in Perinatal CC implementation.²³⁻²⁶

6. Technology enabled services (TES) may offer a solution for effective Perinatal CC delivery.

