TESs can (a) include dashboards/interfaces to automate Care Manager (CM) tasks and streamline CM workflows for population-based case review; (b) connect the CM to both patients and providers, facilitating communication about stepped care among the entire care team; and (c) directly deliver digital treatments to people who are unable to engage in person due to logistical barriers common in the Perinatal period. Smartphones are broadly available among reproductive aged people and are owned by 94% of Americans under age 30 and 89% ages 31-49.²⁷⁻²⁹ Several RCTs have shown that digital interventions delivered through smartphones are effective in reducing Postpartum Depression.³⁰ As such, a TES can integrate a seamless service in which adherence to the core tenets of CC are facilitated by

STU#:00211815

digital technologies, but this novel application of TES has not been previously studied.

STUDY ENDPOINTS

We will utilize a pragmatic, RCT based on our OEI hybrid trial design.⁵³⁻⁵⁵ A total of 85 people (75 from Northwestern and 10 from Women and Infants Hospital) will be randomized to either TES or enhanced treatment as usual (eTAU). Descriptions of the TES and eTAU interventions appear in the next section labeled “Study Intervention(s)/ Investigational Agent(s).” Depressive symptoms and other outcomes will be measured at baseline and at 6 and 12 weeks. Beyond 12 weeks, participants will be allowed to continue use of the TES app and the eTAU website for the duration of the grant-funded budget period. App and website use will be tracked for the entire study duration.

STUDY INTERVENTION(S) / INVESTIGATIONAL AGENT(S)

Participants will be assigned to receive one of two study interventions: (1) a Technology Enabled Service, or (2) Enhanced Treatment as Usual. The design of the TES and eTAU interventions were determined through the design study (STU# STU00211314) and negotiations with our software development contractor (Adaptive Health).

Technology-Enabled Service (TES)

The TES will be based on Adaptive Health’s IntelliCare platform (described below). The TES will permit use of text message communication. Text message content will meet HIPAA standards, and will not contain information that might identify the patient as being in treatment for depression. Text message communication may be used to encourage IntelliCare app use or arrange phone calls to avoid risk of loss of confidentiality.

IntelliCare

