The IntelliCare intervention consists of 2 components: (1) a patient-facing app for assessment and self-management of depression, (2) a Care Manager dashboard. A brief description of each component appears below:

1. Patient-facing app: The patient-facing app contains the following tools for the assessment and self-management of depression:
 - Assessment: Within the IntelliCare App, participants will be prompted to complete an assessment of current (within the prior 2 weeks) depressive and anxiety symptoms.
 - Self-management: IntelliCare depression and anxiety self-management modules will be used in the trial. Each module represents a single behavioral strategy (e.g., scheduling positive behaviors, thought restructuring, goal setting), and takes only a few seconds to use. The modules address specific treatment goals, and may include instructional content as well as interactional components (e.g., activity scheduling/monitoring, thought records) that support behavior change. All participants will download the main app onto their own phones and will be encouraged to use the modules as directed by the CM throughout the study period.
2. Care Manager Dashboard: The CM dashboard displays which modules are being used by which patients, supporting efficient triage and clinical decision making. The dashboard also includes mental health assessment scores, a place to document notes about patient interactions, and a text messaging interface.

Enhanced Treatment as Usual (eTAU)

The eTAU will consist of current care plus access to a website (compass-care.northwestern.edu) that will provide content specific to perinatal depression. Patients randomized to eTAU will communicate with their Care Managers using phone or MyChart, which is consistent with standard clinical practice.

PROCEDURES INVOLVED

This is a multi-pronged prospective investigation of a TES to improve collaborative care service delivery to people with perinatal depression. Participants will be enrolled in a pragmatic RCT with outcome assessments at baseline, 6 and 12 weeks.

Data will be gathered from study participants as outlined in the table below. We have described how data collection methods differ by randomization assignment where applicable.

STU#:00211815

Table 1. Effectiveness Measures

Outcome/Construct	Measure Name	Method	Timing

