Depressive and suicidality symptoms	PHQ-9 with BDI	TES: data gathered via IntelliCare and REDCap eTAU: data gathered routinely for COMPASS clinical care CMs or research team will enter these data in the study database.	Continuous
Anxiety symptoms	GAD-7	TES: data gathered via IntelliCare and REDCap eTAU: data gathered routinely for COMPASS clinical care CMs or research team will enter these data in the study database.	Continuous
Suicidal ideation	Columbia Suicide Risk Assessment	Data gathered routinely for COMPASS clinical care by Care Managers or research team and entered in the study database by the CM or research team	As needed
Demographics	Demographics Questionnaire	Participant self-report survey	0w
Health status	SF-36 (3 items)	Participant self-report survey	0w
Other mental health treatment	“Other Mental Health Treatment” Questionnaire*	Participant self-report survey	0w, 6w, 12w
Technology engagement, usability, usefulness, and satisfaction	TWEETS	Participant self-report survey	6w, 12w
Mobile phone competence	Mobile Phone Competence	Participant self-report survey	0w
Bond between patient and CMs	Working Alliance Inventory / Short Revised (WAI-SR); (BOND ONLY)	Participant self-report survey, Care Manager data entry	6w, 12w
Supportiveness of CMs	Supportive Accountability Inventory	Participant self-report survey	6w, 12w
Satisfaction with services	SIMH	Participant self-report survey	6w, 12w
Coaching user feedback	Coaching user feedback survey	TES only: Participant self-report survey	6w
	Coaching user feedback interview	TES only: Optional participant telephone interview	6w
Usability Interview	Usability Interview	TES only: Optional participant telephone interview	2w, 4w, 6w
Alcohol and Substance Use	Substance use information in the EMR	Medical records	Continuous
Comorbidities	Diagnoses from the EMR	Medical records	Continuous
Obstetrics information	Actual delivery date, complications in pregnancy, gestational age at delivery	Medical records	Continuous

STU#:00211815

Adherence	App/website usage, communication with CM	TES: app usage and text message data gathered by IntelliCare and transferred to the study team eTAU: website usage data gathered via website analytics tools	Continuous

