Execution of Stepped Care	Each time the PHQ-9 score is documented, the CM or the research team will indicate whether the stepped care protocol was executed in response to PHQ-9 total score.	Data gathered routinely for COMPASS clinical care. CMs will enter these data in the study database when documenting PHQ-9 scores.	Continuous

Self-report surveys and Care Mzanager data entry forms have been uploaded to the eIRB+ system for review. Please see the data handling section for a description of the procedures that will be used to obtain data from self-report surveys, interviews, CM data entry, medical record data extraction, IntelliCare data, and COMPASS website usage data.

DATA AND SPECIMEN BANKING

Deidentified data will be stored indefinitely for secondary analyses.

STUDY TIMELINES

Enrollment Timeline

Recruitment for the clinical trial will occur outside the context of usual Care Manager (CM) activities and will be managed by the research team with support from the Care Managers (CM). All patients judged as meeting perinatal depression or anxiety criteria by the research team who are at least 18 years of age will be offered participation and will be screened verbally by the research team and/or Care Managers (CM). If participants screen eligible, they will be directed to a digital version of the consent form, as described on Pg. 12. The research team will record the results of all recruitment contacts. We expect to enroll 100 participants through March 2024.

Timeline of Participant Activities

Active participation will last 12 weeks for each study participant. Participants will use the study interventions during the 12-week period and complete assessments according to the schedule laid out in table 2 below:

Table 2. Participant Activities

Method	Week 0	Week 2	Week 4	Week 6 Mid-Treatment	Week 12 End of Treatment
Self-report Survey	x			x	x
Usability Interview (optional)*		x	x	x	
Coaching User Feedback Interview (optional)*				x	
App and Website Usage	Continuous, unobtrusive				
Communication with Care Manager	Continuous, unobtrusive				
Medical Record Data	Continuous, unobtrusive				

* Optional Usability/User-Feedback Interviews (2w, 4w, 6w)

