Emotional Discomfort: Participants will be informed that their participation in the study is entirely voluntary and that they may stop at any time without affecting their access to medical care. Participants will be told that they may decline to answer any questions or complete any procedures.

Plans for Ensuring Safety and Suicide Prevention: The development of suicidal ideation during the study remains the most serious risk. Patient safety always takes precedence over study protocol. All suicidality procedures are managed directly by the patient's care management team or through research staff including [name], [name], and [name]. The CMs are licensed clinical social workers who have completed Mental Health First Aid trainings and have been trained in suicide risk management as part of their regular job duties. CMs are buttressed by the COMPASS psychiatrists, the obstetricians, and the Asher Center (see Letter of Support from [name]) who are available for clinical support. Research staff are trained in suicide risk management as part of their regular job duties. Research staff are buttressed by clinical psychologists and are available for clinical support.

There are a number of pathways through which suicidal risk can be detected. During the trial phases, suicidality is detected through automated PHQ-9 self-report assessments, direct communications with the Care Managers via phone or messaging (email, text, etc.), or direct communication with research staff during user feedback interviews. In each of these instances, the goal is to rapidly acquire additional information that can trigger safety procedures if necessary. When suicidality is expressed by the participant directly to the research staff in a usability interview or other direct communication, the research staff follows up to conduct a risk assessment based on the Columbia Suicide Severity Rating Scale and engage the participant in risk management procedures based on their risk status.

All participants in the trial or pre-enrollment receive automated self-report assessments. If a participant rates Question 9 of the Patient Health Questionnaire-9 (i.e., "Over the last 2 weeks, how often have you

STU#:00211815

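### Table 1 gives the PHQ-9 and GAD-7 arm-specific sources, and neither analysis plan confines the analysis to a score common to both arms

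*Protocol*

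**What the plan says.** - Protocol, Objectives: depression severity is the primary outcome and anxiety a secondary one. On masking: "It is not feasible to mask participants or providers".
- Protocol, Table 1, PHQ-9 and GAD-7 rows: "TES: data gathered via IntelliCare and REDCap eTAU: data gathered routinely for COMPASS clinical care". Timing in both rows is given as continuous. The lead-in to the table says: "We have described how data collection methods differ by randomization assignment where applicable".
- Protocol, Study Endpoints: "Depressive symptoms and other outcomes will be measured at baseline and at 6 and 12 weeks". Procedures Involved says the same: "Participants will be enrolled in a pragmatic RCT with outcome assessments at baseline, 6 and 12 weeks".
- Protocol, description of the patient-facing app: "Within the IntelliCare App, participants will be prompted to complete an assessment of current (within the prior 2 weeks) depressive and anxiety symptoms".
- Protocol, Plans for Ensuring Safety and Suicide Prevention: "All participants in the trial or pre-enrollment receive automated self-report assessments". The same section refers to automated PHQ-9 self-report and sets out what follows from an answer to its ninth item.
- Protocol, Data Analysis Plan, and SAP, Effectiveness: a generalized linear mixed model compares the arms over time, with multiple imputation for missing data. Both documents also plan moderation models for the end-of-treatment depression score. Table 2 labels its last column "Week 12 End of Treatment".

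**The concern.** A between-arm comparison of a self-reported symptom score is cleanest when the score is obtained in the same way, at the same times, in both arms. Table 1 describes something else for the primary outcome: a digital research and app route in one arm, and whatever clinical care produces in the other.

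Scores given to a care manager in a clinical contact and scores typed into an app or survey may differ in level. They may also be taken at different times and be missing for different reasons. In an unmasked trial, any such difference lines up with treatment and cannot be told apart from a treatment effect by looking at the scores.

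If the analysis plan does not name the score to be used, the choice among several available scores is also left open until the data have been seen.

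**Working it through.** No figure in the documents bears on this point, so there is no number to reproduce. The check sets the texts side by side.

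1. **Which score is at issue.** The PHQ-9 (with an added BDI suicidality question) is the only depression scale in Table 1, and both power texts are in PHQ-9 points. It is the primary outcome measure. The GAD-7 is the anxiety measure.

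2. **What Table 1 says, read literally.** TES has two channels, IntelliCare and REDCap. eTAU has routine COMPASS care. The lead-in shows that differences by arm are intended, so this is not a product of broken table text. The same table marks other measures as participant surveys at fixed weeks: other mental health treatment at 0, 6 and 12 weeks, and TWEETS and SIMH at 6 and 12 weeks. The PHQ-9 and GAD-7 rows carry neither that label nor those weeks.

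3. **What points to a common score.** Study Endpoints and Procedures Involved schedule outcomes at baseline, 6 and 12 weeks. In Table 2 the only method at exactly those weeks is the self-report survey, and Table 3 pays all participants for it. The safety section describes an automated PHQ-9 and says automated self-report reaches every participant, including before enrolment, when nobody is described as having the app. Consent Process gives consented participants a link to baseline self-report measures. Together these make a PHQ-9 common to both arms probable. The safety text does not name the GAD-7, so the case there is weaker. No text states that the week 0, 6 and 12 survey contains either scale; the survey forms were uploaded to eIRB+ and are not in these documents.

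4. **Whether more than one score per participant is foreseen.** Yes. TES has two channels. Care managers and research staff routinely enter depression and anxiety assessments in REDCap. Table 1 records stepped-care execution at every documented PHQ-9. Table 5 lists PHQ-9 and GAD-7 responses held by the app vendor.

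5. **Whether the analysis texts choose.** They do not. Neither mixed-model text names a source, a visit window or a rule for several scores, and neither says how time is coded. The added covariates concern changes made through optimization. The SAP's propensity adjustment concerns patient characteristics. Neither covers how a score was obtained. The moderation models need one end-of-treatment score, which has a nominal week (12) but no source or window.

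6. **What follows.** Write the observed arm difference as the true difference plus (source effect in TES − source effect in eTAU). With one source for both arms, the source part of that bracket drops out; the effect of unmasking on self-report remains. With Table 1's sources the bracket is unknown. Multiple imputation fills in missing scores from a model fitted to the observed ones, so it carries the bracket forward and does not remove it.

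**The case against.** The strongest reply is that a common PHQ-9 is the natural reading of the protocol as a whole: outcomes are scheduled at three fixed weeks, a survey runs at exactly those weeks in both arms, and the safety section sends automated self-report to everyone. Continuous clinical scoring could simply run alongside it. This largely stands for the PHQ-9, and less so for the GAD-7. It does not close the gap, because the safety text is not an outcome definition, it does not match Table 1's eTAU entry, and no analysis text limits the model to that score.

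A second reply is that a mixed model can use every score at its actual date, so a single selected score is not essential. That is true of the method, but neither document says it will be used that way. It would also leave the source difference in place, and the moderation models would still need one defined score.

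A reader might go further and infer any of the following. The documents do not support them:

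- **That eTAU has no research self-report PHQ-9.** The safety section points the other way.
- **That TES scores depend only on app prompts.** Table 1 lists REDCap for TES as well.
- **That care managers enter scores in one arm only.** The flattened Table 1 cell does not show whether its last sentence covers one arm or both.

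**Conclusion.** The point holds as a specification and reconciliation gap that should be fixed before analysis. Table 1 states arm-specific sources for the primary and anxiety scales, other sections imply a common score, and neither analysis plan says which governs. If Table 1 governs, the source of the analysed score can differ by arm, and so possibly can its timing and completeness.

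No size or direction can be given. The documents contain no estimate of a source effect, and the effect on the contrast would depend on whether the difference was also present at baseline. A reader might infer that the trial's result will be biased. The documents show only that the plan permits it.

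The conclusion assumes that the forms in eIRB+ do not themselves serve as an analysis rule. They could show that the items are collected in both arms, which would reduce the fix to wording.

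**What to change.** **Define the endpoints.** Before analysis, state in the SAP that the depression and anxiety endpoints are the self-report PHQ-9 and GAD-7 from the REDCap survey at weeks 0, 6 and 12 in both arms. Give one visit window and one rule for several scores, the same for both arms. Reconcile Table 1 with Study Endpoints, Procedures Involved and the safety section.

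**If the items are not in that survey for eTAU.** Add them for participants still in follow-up. For those who have finished, do not mix sources according to availability: Table 1 lists REDCap only for TES, so that would bring the arm difference back. Use the type of source obtainable in both arms, with the same window. Report source, timing and missingness by arm. If no common source exists, state the source difference as a limitation. Keep the remaining app and clinic scores for sensitivity analyses or as auxiliary variables in the imputation.

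**Cost.** If the scores already exist in both arms, only wording. Otherwise 9 + 7 = 16 short items on a survey that is already paid for, with ninth-item answers handled under the existing safety text. Some app or clinic scores leave the main analysis. Adding items may help few participants. If enrolment ended on 31 March 2024, the last week-12 date is 84 days later, 23 June 2024. At the SAP date of 15 April 2024, only those enrolled after about 22 January 2024 (84 days earlier) still had week 12 ahead. Naming the source, window and rule remains possible until the primary analyses, which the protocol expects to complete by 31 March 2025.

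Separately, the protocol's power text refers to PHQ-9 scores at 12 months in a 12-week schedule. That wording should be corrected, but it does not bear on this point.
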